### Sample size determination for SCLC expansion cohort

In Amendment 09, in addition to the original two-stage design of SCLC subjects, additional SCLC expansion cohort subjects will be randomized in a 3:2 ratio to one of 2 expansion groups: Arm A (150 subjects, nivolumab mono) or Arm B (100 subjects, nivolumab 1 mg/kg + ipilimumab 3 mg/kg) and will be stratified for number of prior treatment lines (1 vs 2 prior chemotherapy regimens).

Based on SCLC data so far observed in this study with an ORR of about 18% for nivolumab monotherapy, a sample size of  $N = 150$  will target a Type I error rate of 5% and will have 84% power to reject the null hypothesis ( $ORR \leq 10\%$ ) if the true response rate is 18%. An ORR of  $> 10\%$  is considered a clinically meaningful result in a study population of second- and third-line SCLC patients.

Based on SCLC data so far observed in this study with an ORR of about 30% for nivolumab / ipilimumab combination therapy, a sample size of  $N = 100$  will target a Type I error rate of 5% and will have 83% power to reject the null hypothesis ( $ORR \leq 18\%$ ) if the true response rate is

30%. An ORR of > 18% is considered a clinically meaningful result for a nivolumab / ipilimumab combination in a study population of second- and third-line SCLC patients which outweighs the potential for higher toxicity to be anticipated for this cohort.

*Sample size determination for ovarian cancer cohort*

Also in Amendment 09, ovarian cancer cohort is added and one stage design with the treatment of 40 subjects for each arm will be used. These sample sizes will provide 79% power to reject the null hypothesis of 10% response rate if the true response rate is 25% with a two-sided Type I error rate of 5%.

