## **4 ENDPOINTS**

### **4.1 Primary**

#### **4.1.1 Objective Response Rate**

The primary endpoint is the objective response rate (ORR). The ORR is defined as the number of subjects with a best overall response (BOR) of complete response (CR) or partial response (PR) divided by the number of treated subjects. The BOR is defined as the best response designation, as determined by the investigator, recorded between the date of treatment assignment and the date of objectively documented progression per RECIST 1.1 or the start date of subsequent anti-cancer therapy, whichever occurs first. CR or PR determinations included in the BOR assessment must be confirmed by a second scan no less than 4 weeks after the criteria for response are first met. For subjects without documented progression or subsequent therapy, all available response designations will contribute to the BOR assessment. For subjects who continue treatment beyond progression, the BOR should be determined based on response designations recorded up to the time of the initial RECIST 1.1-defined progression.

These measures of response will be interpreted in the context of historical responses observed following treatment with approved agents.

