### Sample size determination for bladder cancer cohort

In Amendment 06, bladder cohort is added. One stage design with the treatment of 60-100 subjects is used. These sample sizes provide 90% to 97% power to reject the null hypothesis of 10% response rate if the true response rate is 25% with a two-sided Type I error rate of 5%.

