## **7 STATISTICAL ANALYSES**

### **7.1 General Methods**

Unless otherwise noted, the following subsections describe tabulations of discrete variables, by the frequency and proportion of subjects falling into each category, grouped by cohort (with total). Percentages given in these tables will be rounded and, therefore, may not always sum to 100%. Continuous variables will be summarized by cohort (with total) using the mean, standard deviation, median, minimum and maximum values.

Time to event distributions (i.e. overall survival, progression free survival, time to response, and duration of response) will be estimated using Kaplan Meier techniques. When appropriate, the median along with 95% CI will be provided using Brookmeyer and Crowley methodology (using the log-log transformation for construction of confidence intervals). Rates at fixed timepoints (e.g. OS at 12 months) will be derived from the Kaplan Meier estimate along with their

corresponding log-log transformed 95% confidence intervals. Confidence intervals for binomial proportions will be derived using the Clopper-Pearson method.

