### **7.5.1 Objective Response Rate**

#### **7.5.1.1 Primary Analysis**

ORR will be summarized for each cohort by a binomial response rate and corresponding two-sided 95% exact CI using the method proposed by Atkinson and Brown for cohorts using two-stage design and Clopper and Pearson method for cohorts using one stage design.

DOR will be summarized for subjects who achieve confirmed PR or CR using the Kaplan-Meier product-limit method. Median values of DOR, along with two-sided 95% CI using the log-log transformation will also be calculated by cohort. In addition, the percentage of responders still in response at different time points (3, 6, and 12 months) will be presented based on the KM plot.

For SCLC expansion cohorts, similar methods will be used to summarize ORR and DOR for each stratification factor.

The magnitude of reduction in tumor burden will be summarized descriptively.

For the analyses of crossover subjects during original assigned treatments, ORR data will be truncated prior to the first crossover dose date. For the analysis of crossover subjects during crossover period, ORR will also be summarized. Baseline will be re-established. BOR, PR, and CR will be re-derived starting on the date of crossover.

In addition, percent change from baseline based on the target lesions will be plotted overtime for each subject grouped by treatment arm (spider plot). For crossover subjects, data will be truncated prior to the first date of crossover.

Time on therapy and time to response will also be plotted for each subject with symbols indicating time of radiographic progression, LKDA, first response, last dose, last dose when subject off treatment, crossover, and death (swimmer plot). For crossover subjects, no data will be truncated.

- A plot of individual time course of tumor burden change per investigator assessment but limited to subjects who were treated beyond progression.

Among subjects treated beyond progression, non-conventional benefitters will be identified and will be defined as subjects who had not experienced a BOR of PR/CR prior to initial RECIST-defined progression, and met at least one of the following:

- Criterion 1: Appearance of a new lesion followed by decrease from baseline of at least 10% in the sum of the target lesions.
- Criterion 2: Initial increase from nadir  $\geq 20\%$  in the sum of the target lesions followed by reduction from baseline of at least 30%.

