#### **7.5.4 Interim Analyses**

Data will be reviewed during the Dose Escalation Safety Evaluation Phase to determine the maximum tolerated dose level for arm N-I and to make decisions about Stage 2 for each cohort. The decision to proceed from Stage 1 to Stage 2 will be conducted for TNBC, GC, PC, and SCLC treatment arms with two-stage design independently.

Interim analyses may be conducted after Stage 1, by cohort. These interim analyses may be triggered if a “super” response (i.e. 8 or more responders out of 18 subjects) is observed or if it is necessary in order to make decisions regarding further development and supporting external disclosure such as medical conference. Summaries and listings of efficacy and safety will be provided. This interim analysis will not impact the study duration and the trial will continue as planned.

For BC and OC cohorts, one-stage design is used. The interim analysis will be conducted by cohort to support internal decision making and publication disclosure.

For new SCLC expansion cohorts, no interim analysis will be performed.

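### The ovarian cohort's stated 79% power is not what 40 subjects per arm deliver under the SAP's own exact method: it is 70%

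*SAP*

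**What the plan says.** All references are to the main SAP (version 2.0).

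- **Design.** Section 5, under the ovarian cohort: "ovarian cancer cohort is added and one stage design with the treatment of 40 subjects for each arm will be used". Section 7.5.4 confirms it: "For BC and OC cohorts, one-stage design is used". Section 2.2 lists three ovarian arms of 40.
- **Power.** Section 5: "These sample sizes will provide 79% power to reject the null hypothesis of 10% response rate if the true response rate is 25"%. The same sentence sets a two-sided Type I error of 5%. No test, formula or responder threshold is given.
- **Analysis.** Section 7.5.1.1 summarises response rate with a two-sided 95% exact interval, using the "Clopper and Pearson method for cohorts using one stage design". Section 7.1 makes this the general rule: "Confidence intervals for binomial proportions will be derived using the Clopper-Pearson method".
- **Denominator.** Section 4.1.1 defines the response rate as responders "divided by the number of treated subjects", so the full 40 treated subjects count.
- **Bladder.** Section 5 makes a parallel statement for 60 to 100 subjects: "These sample sizes provide 90% to 97% power to reject the null hypothesis of 10% response rate", also against 25% at two-sided 5%.

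**The concern.** The power figure and the planned analysis do not belong to the same procedure. With only 40 binary outcomes the exact interval moves in coarse steps, and a smooth large-sample formula can differ from it by several points. A power statement should describe the procedure that will be applied to the data.

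Two things are at stake. First, each ovarian arm is presented as missing a regimen with a 25% response rate about one time in five, when under the planned interval it is three times in ten. Second, no responder count is stated, so the boundary result is ambiguous. An observed 8/40 (20%) rejects 10% under the normal approximation but not under the Clopper-Pearson interval, and the choice could be made after the data are seen.

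**Working it through.** **Inputs.** n = 40 treated per arm, p0 = 0.10, p1 = 0.25, two-sided alpha 5%, stated power 79% (all Section 5); exact two-sided 95% Clopper-Pearson interval (Sections 7.1 and 7.5.1.1).

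**Step 1: reproduce the stated figure.** One-sample normal approximation, with the null variance at the critical value and the alternative variance for power:

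Power = Φ{ [p1 − p0 − 1.96·√(p0(1−p0)/n)] / √(p1(1−p1)/n) }

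- √(0.10·0.90/40) = 0.0474, and times 1.96 this is 0.0930
- √(0.25·0.75/40) = 0.0685
- Power = Φ{(0.15 − 0.0930)/0.0685} = Φ(0.833) = 79.8%

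This gives the stated 79% if truncated. Other two-sided variants are further away: continuity-corrected 74.2%, arcsine 72.3%, alternative variance only 59.1%, null variance only 88.5%.

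The same formula, truncated, also fits three other figures in Section 5: 84.6% (stated 84%) and 83.5% (stated 83%) for the two SCLC expansion arms, and 90.7% (stated 90%) for bladder with 60 subjects. It does not fit the upper bladder figure: 98.2% at n = 100, against 97% stated.

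**Step 2: the planned method at n = 40.** X is the number of responders.

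| Responders | Clopper-Pearson lower limit | P(X ≥ x) at 10% | P(X ≥ x) at 25% |
|---|---|---|---|
| 8/40 | 9.05% | 4.19% | 81.8% |
| 9/40 | 10.84% | 1.55% | **70.0%** |
| 10/40 | 12.69% | 0.51% | 56.0% |

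The lower limit first exceeds 10% at 9/40. Power is P(X ≥ 9 | n = 40, p = 0.25) = 70.0%, so the false-negative risk is 100% − 70.0% = 30.0%, against 100% − 79% = 21% as stated. No cut-off at n = 40 gives 79%.

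**Step 3: is 70% peculiar to Clopper-Pearson?** At n = 40, no. The minimum-likelihood two-sided exact test and the mid-p version also reject upward only from 9/40, with power 70.0%.

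**Step 4: does the normal test hold its level?** At n = 40 it rejects from 8/40 (z = (0.20 − 0.10)/0.0474 = 2.11) and also at 0/40 (z = −2.11). Its true two-sided size is P(X ≥ 8 | 0.10) + P(X = 0 | 0.10) = 4.19% + 1.48% = 5.67%, above the stated 5%.

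**Step 5: size that would support the claim.** Exact power is saw-toothed in n. Under the Clopper-Pearson rule, 79% is first reached at n = 48 (at least 10 responders, 79.5%) and is exceeded at every n only from 53 (at least 11 responders, 80.7% at n = 53).

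**Step 6: bladder.**

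| n | First count excluding 10% | Lower limit there | Lower limit one below | Exact power at 25% | Stated |
|---|---|---|---|---|---|
| 60 | 12 | 10.78% | 9.52% (11/60) | 85.2% | 90% |
| 100 | 17 | 10.23% | 9.43% (16/100) | 97.9% | 97% |

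Only the lower end is overstated. Unlike at n = 40, the choice of exact method matters at n = 60: the minimum-likelihood test rejects from 11/60 with 91.4% power and a size of 4.80%. The 85.2% is therefore specific to Clopper-Pearson, which is the method the SAP names.

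**The case against.** The strongest reply is that the SAP never says the interval is the test. Section 7.5.1.1 describes a summary, Section 4.1.1 says responses will be read against historical rates, and no ovarian go/no-go rule depends on 8 versus 9 responders. Planning with a normal approximation and reporting an exact interval is common. If the approximate test were itself the decision rule, rejection would begin at 8/40 and power would be 81.8%, so 79% would not be overstated.

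Part of this stands. The rejection rule is inferred, and so is the origin of 79%: the SAP names no formula, the match needs truncation, and the same formula misses the upper bladder figure. The practical consequence is limited to how the result is interpreted. It is also true that Section 2.1 gives bladder arms of 26 to 105 subjects, so 60 is the lower end of the Section 5 range and not a fixed arm size.

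The rest does not rescue the figure. Section 5 itself speaks of power to reject a null hypothesis at two-sided 5%, and the two-sided 95% exact interval is the only procedure offered that could do so. Rejecting from 8/40 has a true size of 5.67%, which breaks the stated level. Reading it as one-sided 5% (at least 8/40, 4.19%, power 81.8%) contradicts the word two-sided. The correction does not depend on where 79% came from.

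**Conclusion.** The concern holds. Under the SAP's own method, 40 subjects per ovarian arm give 70.0% power at a true response rate of 25%, not 79%: a shortfall of nine points, with a false-negative risk of 30% per arm in place of 21%. For a bladder arm of 60 the figure is 85.2%, not 90%; the 97% at 100 subjects is sound.

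This assumes that the null is rejected when the two-sided 95% Clopper-Pearson interval lies above 10%, and that all 40 treated subjects are in the denominator, as Section 4.1.1 requires. The planned estimates and intervals remain valid. What is wrong is the stated operating characteristic and the missing threshold, so this should be corrected but does not undermine the analysis.

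**What to change.** In Section 5, replace the ovarian power sentence with wording such as: *With 40 treated subjects per arm, the two-sided exact 95% confidence interval for the response rate excludes 10% when at least 9 subjects respond; the power is 70% if the true response rate is 25%.*

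For bladder, restate any 60-subject arm as needing at least 12/60 responders, with 85% power. The figure for 100 subjects can stay, with its threshold of 17/100 added.

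If the sponsor intended a different rejection rule, the SAP should name it, with its responder threshold and true Type I error.

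The cost is SAP wording only. A stated figure becomes less favourable, no patients are added, and the planned interval does not change.

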## **6 STUDY PERIODS, TREATMENT REGIMENS AND POPULATIONS FOR ANALYSES**

### **6.1 Study Periods**

#### **6.1.1 Baseline Period**

Baseline evaluations or events will be defined as evaluations or events that occur before the date and time of the first dose of study treatment.

In cases where the time (onset time of event or evaluation time and dosing time) is missing or not collected, the following definitions will apply:

- Pre-treatment AEs will be defined as AEs with an onset date prior to but not including the day of the first dose of study treatment
- Baseline evaluations (laboratory tests, pulse oximetry and vital signs) will be defined as evaluations with a date on or prior to the day of first dose of study treatment

If there are multiple valid assessments, the assessment that is closest to day (and time if collected) of the first dose of study treatment will be used as the baseline in the analyses. If multiple assessments are collected at the same date (and time if collected), the assessment with the latest database entry date (and time if collected) will be considered as baseline.

#### **6.1.2 Post Baseline Period**

On-treatment AEs will be defined as AEs with an onset date and time on or after the date and time of the first dose of study treatment (or with an onset date on or after the day of first dose of study treatment if time is not collected or is missing). An AE will be counted as on-treatment if the event occurred within 30/100 days of the last dose of study treatment.

On-treatment evaluations (laboratory tests, pulse oximetry, and vital signs) will be defined as evaluations taken after the day (and time, if collected and not missing) of first dose of study treatment. An evaluation will be counted as on-treatment if it occurred within 30/100 days of the last dose of study treatment.

### **6.2 Treatment Regimens**

The treatment group “**as assigned**” will be retrieved from the IVRS system

The treatment group “**as treated**” will be the same as the arm as assigned by IVRS. However, if a subject received the incorrect drug for **the entire period** of treatment, the subject’s treatment group will be defined as the incorrect drug the subject actually received.

### **6.3 Populations for Analyses**

- **Enrolled Subjects:** All subjects who signed an informed consent form and were registered into the IVRS.
- **Assigned Subjects:** All subjects who were assigned to the highest tested tolerated dose level in the Dose Escalating Safety Evaluation Phase or to any treatment group during the Staged Enrollment Phase.
- **All Treated Subjects:** All subjects who received at least one dose of any study medication.
- **All Response Evaluable Subjects:** A subject will be part of the response evaluable subject if the following criteria are met:
  - a) BOR is in (CR, PR, SD or PD),
  - b) at least one target lesion identified at baseline,
  - c) at least at one on-study timepoint with target lesion assessment (non missing percent change from baseline).
- **All PK Subjects:** All assigned subjects with available serum time-concentration data.
- **Immunogenicity Subjects:** All treated subjects with baseline and at least 1 post baseline immunogenicity assessment.
- **Crossover Subjects:** All treated subjects who crossed over from Arm N to Arm N-I.
- **All PD-L1 tested subjects:** All subjects who had a tumor tissue sample available for assessment of PD-L1 expression at baseline.
- **All Treated PD-L1 tested subjects:** All PD-L1 tested subjects who received at least one dose of study treatment.
- **PD-L1 evaluable subjects:** All treated, PD-L1 tested subjects with quantifiable PD-L1 expression.

## **7 STATISTICAL ANALYSES**

### **7.1 General Methods**

Unless otherwise noted, the following subsections describe tabulations of discrete variables, by the frequency and proportion of subjects falling into each category, grouped by cohort (with total). Percentages given in these tables will be rounded and, therefore, may not always sum to 100%. Continuous variables will be summarized by cohort (with total) using the mean, standard deviation, median, minimum and maximum values.

Time to event distributions (i.e. overall survival, progression free survival, time to response, and duration of response) will be estimated using Kaplan Meier techniques. When appropriate, the median along with 95% CI will be provided using Brookmeyer and Crowley methodology (using the log-log transformation for construction of confidence intervals). Rates at fixed timepoints (e.g. OS at 12 months) will be derived from the Kaplan Meier estimate along with their

corresponding log-log transformed 95% confidence intervals. Confidence intervals for binomial proportions will be derived using the Clopper-Pearson method.

## **7.2 Study Conduct**

### **7.2.1 Accrual**

The following will be presented on the enrolled population:

- Number of subjects accrued by country and investigational site
- Number of subjects accrued by month

### **7.2.2 Relevant Protocol Deviations**

The following programmable deviations will be considered as relevant protocol deviations and summarized by treatment group, tumor type, and overall. Non-programmable relevant eligibility and on-treatment protocol deviations, as well as significant (both programmable and non-programmable) eligibility and on-treatment protocol deviations will be reported through ClinSIGHT listings.

#### At Entrance:

- Subjects with baseline ECOG performance status > 1
- Subjects without measurable disease at baseline

#### On-study:

- Subjects receiving anti-cancer therapy (chemotherapy, radiotherapy, hormonal therapy, immunotherapy, standard or investigational agents for treatment of cancer) while on study therapy.
- Subjects treated differently than as assigned (subjects who received the wrong treatment, excluding the never treated).

Listings will also be provided.

## **7.3 Study Population**

### **7.3.1 Subject Disposition**

The total number of subjects enrolled (assigned or not assigned) will be presented along with the reason for not being assigned. This analysis will be performed on the all enrolled population only.

Number of subjects who discontinued study treatment along with corresponding reason will be tabulated by cohort as treated. Reason for discontinuation will be derived from subject status CRF page. This analysis will be performed only on the all treated subjects population.

Number of subjects assigned but not treated along with the reason will be tabulated by treatment cohort as assigned. This analysis will be performed on the all assigned population only.

A subject list for all treated subjects will be provided showing the subject's randomization date, first and last dosing date, off study date and reason for going off-study.

### 7.3.2 **Demographics and Baseline Characteristics**

The following baseline characteristics will be summarized by cohort for all treated subjects. All baseline presentations identify subjects with missing measurements. In tabulations of categorical variables, percents are based on subjects with measurements. Listings will also be provided.

- Age (descriptive statistics)
- Age category (< 65, ≥ 65 - < 75, ≥ 75 - < 85, ≥ 65, ≥ 75, ≥ 85)
- Gender (male/female)
- Race (white/black/asian/other)
- Region (US, Europe)
- ECOG Performance Status (0/1)
- Weight (descriptive statistics)
- Baseline LDH (≤ULN, >ULN)
- Baseline LDH (≤2\*ULN, >2\*ULN)
- History of Brain Metastases (Yes/No)
- Baseline liver metastases (yes/no)
- Baseline visceral metastases (lung, liver and bone) (yes/no)
- Baseline lymph node only (yes/no)
- Baseline Hemoglobin (< 10g/dL vs. ≥ 10g/dL)
- Baseline Creatinine Clearance (CrCL) (< 30, 30 - < 60, ≥ 60ml/min)

The creatinine clearance will be calculated using Cockcroft-Gault formula, defined as:

Formula 1:

$$\text{CrCL(ml/min)} = \frac{(140 - \text{age (in years)}) * \text{weight (in kg)}}{72 * \text{serum creatinine (in mg/dL)}}$$

for males and

Formula 2:

$$\text{CrCL(ml/min)} = \frac{(140 - \text{age (in years)}) * \text{weight (in kg)}}{72 * \text{serum creatinine (in mg/dL)}} * 0.85$$

for females. Baseline weight will be used.

- Time from Initial Disease Diagnosis to Assignment (<1 year, 1-<2 year, 2-<3 year, 3-<4 year, 4-<5 year, ≥5 year)
- All lesions (Investigator Tumor Assessments at Baseline): sites of disease, number of disease sites per subject
- Target lesions (Investigator Tumor Assessments at Baseline): Presence of target lesions, site of target lesion, sum of longest diameter of target lesion
- Platinum resistant/refractory versus platinum sensitive (SCLC only) and Platinum-refractory versus platinum resistant vs platinum sensitive (OC only)
- Smoking status (SCLC only)

